### Adverse Event of Special Interest (AESI)

AESIs for lerapoltrev are defined as cerebral spinal fluid leakage, aseptic meningitis, cerebral edema (CE), peritumoral edema (PTE).

### irAE

An AE of immunologic etiology associated with pembrolizumab

### Dose limiting toxicity (DLT)

DLTs are defined per protocol as any of the following events related to lerapoltrev:

- 1)  $\geq$  Grade 3 neurologic events related to PTE or CE within the first 3 weeks of the first pembrolizumab administration that:
  - a) Do not resolve to  $\leq$  Grade 1 with the management practices outlined herein ( $\leq$  4mg/dexamethasone or 7.5 mg/kg bevacizumab) within 3 weeks of initiating such treatments,  
and/or
  - b) Require surgical debulking of the PVSRIPO infused tumor within 3 weeks of the first pembrolizumab administration
- 2) Any of the following SAEs:
  - a) Treatment-related death
  - b) Treatment-related life-threatening event
  - c) A medically significant condition (defined as an event that compromises patient safety or may require medical or surgical intervention to prevent one of the outcomes above).
  - d) Requires inpatient hospitalization or prolongation of existing hospitalization
  - e) Results in persistent or significant incapacity or substantial disruption to conduct normal life functions
- 3) Any Grade 4 non-hematologic toxicity
- 4) Any Grade 3 non-laboratory-based toxicity that is not reversible to its pre-PVSRIPO treatment baseline within 2 weeks of onset with the following exceptions:
  - a) Grade 3 fatigue lasting  $\leq$  3 days or Grade 3 fatigue in a participant with Grade 1 fatigue at baseline
  - b) Grade 3 diarrhea, nausea, or vomiting without use of anti-emetics or anti-diarrheals per standard of care
  - c) Grade 3 adrenal insufficiency due to suboptimal steroid replacement therapy
  - d) Grade 3 rash without use of corticosteroids or anti-inflammatory agents per standard of care
- 5) Grade 3 or Grade 4 non-hematological laboratory values only if meets one of the serious criteria outlined in 1 above or
  - a) the abnormality persists for  $>$  1 week
  - b) The abnormality results in a drug-induced liver injury
- 6) Febrile neutropenia meeting following criteria:

Note: Treatment-emergent, non-clinically significant laboratory abnormalities that are treatable with routine measures, or reversible ( $\leq$  1 week of onset) laboratory abnormalities in and of themselves (including liver function tests, uric acid, etc.), are not considered DLTs.

Exceptions (these laboratory values are DLT):

- Grade 4 thrombocytopenia of any duration
- Grade 3 thrombocytopenia associated with bleeding requiring a platelet transfusion

- 5) Febrile neutropenia meeting following criteria:

- a) Grade 3: ANC < 1000/ $\mu$ l with a single temperature of  $> 38.3^{\circ}$  C ( $101^{\circ}$  F) or a sustained temperature of  $\geq 38^{\circ}$  C ( $100.4^{\circ}$  F) for  $\geq 1$  hour
- b) Grade 4: ANC < 1000/ $\mu$ l with a single temperature of  $> 38.3^{\circ}$  C ( $101^{\circ}$  F) or a sustained temperature of  $\geq 38^{\circ}$  C ( $100.4^{\circ}$  F) for  $\geq 1$  h, with life-threatening consequences and urgent intervention indicated

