	
The study will begin with a safety lead-in for evaluation of dose-limiting toxicity (DLT) of the combination prior to full open enrollment. As such, the first 3 patients will be sequentially enrolled with a mandatory waiting period of 21 to 28 days after the immediate prior patient's PVSRIPO infusion to allow for DLT assessment. The DLT evaluation period will begin once a patient receives PVSRIPO followed by the first dose of pembrolizumab and continue for 21 days after the first dose of pembrolizumab (<math>\pm</math> 3 days to account for weekends, patient visit scheduling issues, etc.). The initial DLT assessment will be based on the first 3 patients, which may be expanded up to 6 patients if any DLT are noted in the first 3 (see Sections 3 and 7.4 for additional detail regarding DLT assessment).
 
The first planned dose of pembrolizumab at Week 2 will be delayed by up to 2 additional weeks in patients with any ongoing <math>\geq</math> Grade 3 peritumoral edema (PTE) or cerebral edema (CE) or <math>\geq</math> Grade 2 AEs related to PTE or CE following PVSRIPO infusion or signs or symptoms related to these events that require active treatment (eg, treatment-emergent or worsening events such as hemiparesis requiring <math>\leq</math> 4 mg/day dexamethasone or seizure requiring anti-epileptics; see Section 5.7.2), until such events resolve to <math>\leq</math> Grade 1. If such events have not resolved to <math>\leq</math> Grade 1 by Week 4 post-PVSRIPO infusion, the patient will not receive pembrolizumab under this trial and will be replaced. Pembrolizumab may be administered any time between Weeks 2 and 4 once events resolve as outlined above, as applicable. The first planned pembrolizumab treatment may also be delayed for administrative or other reasons, including other TEAE that in the Investigator's opinion warrants delayed pembrolizumab treatment, but the first pembrolizumab treatment must occur by Week 4 post-PVSRIPO infusion, as noted above.
 
In addition, if a patient requires <math>></math> 4 mg/day of dexamethasone or equivalent prior to the first dose of pembrolizumab, the patient will not receive pembrolizumab under this trial and will be replaced. These replaced patients will not be considered in the initial DLT assessment of the combination but will be eligible for additional follow-up in this study and will be summarized separately from those receiving the combination. Their information may be utilized in exploratory comparative summaries relative to patients treated with PVSRIPO and <math>\geq</math> 1 dose of pembrolizumab in this study.
 
If <math>\leq</math> 33% of the initial participants in the safety lead in (<math>\leq</math> 1 of 3 or if <math>></math> 1 patient of the first 3 experiences a DLT and 3 additional patients are included for DLT assessment, <math>\leq</math> 2 of 6 patients) experience a DLT, the twenty-four remaining participants will be enrolled. If <math>></math> 33% of participants (ie, <math>\geq</math> 3 of 6) experience a DLT, the study will be halted, and the treatment plan modified, or the study may be closed. After the DLT evaluation period and the study is open to full enrollment, ongoing monitoring of TEAEs will occur on at least a monthly basis.

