### 7.1 Adverse Events

An AE is an untoward or medical occurrence associated with the use of study treatment (drug, biologic, or device) in clinical investigation participants, which does not necessarily have a causal relationship with the study treatment. An AE can therefore be any unfavorable and unintended symptom, sign, disease or condition, or test abnormality (although diagnosis should always be reported as the AE if known) regardless of the relationship to study treatment. AEs that do not meet the definition for an SAE are considered non-serious AEs. All AEs must be recorded in the patient's source documents and AE case report form.

AEs will be assessed according to the CTCAE v5. If CTCAE grading does not exist for an AE, the severity of the AE will be graded as mild (1), moderate (2), severe (3), life-threatening (4), or fatal (5).

All AEs will be followed until the outcome is determined by the Investigator as one of the following:

- Resolved
- Ongoing
- Chronic/Stable
- Death
- Unknown

Attribution of AEs/SAEs will be determined for each study intervention or concomitant medication/intervention, as applicable (ie, catheter placement, PVSRIPO, pembrolizumab, corticosteroids, bevacizumab).

Attribution of AEs will be indicated as follows:

- Definite: The AE is clearly related to the study drug(s)

- Probably: The AE is likely related to the study drug(s)
- Possible: The AE may be related to the study drug(s)
- Unlikely: The AE is doubtfully related to the study drug(s)
- Unrelated: The AE is clearly NOT related to the study drug(s)

Events that do not meet the definition of an AE include:

- Non-clinically significant (as assessed by the investigator), isolated, laboratory values, other than those noted in **Section 7.4**; see **Section 7.1.1** for assessing clinical significance of laboratory abnormalities for AE reporting.
- Medical or surgical procedures (eg, endoscopy, appendectomy).
  - Note: The condition that leads to the procedure can be an AE.
- Situations where an untoward medical occurrence did not occur (eg, social and/or convenience admission to a hospital).
- Anticipated day-to-day fluctuations of preexisting diseases/conditions present at baseline that do not worsen.
- Planned hospital admissions or surgical procedures for elective procedures or for an illness or disease that existed before the signing of the ICF or before the participant was enrolled in the study will not be captured as TEAEs/SAEs.

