**7.4 Assessment and Definition of Dose Limiting Toxicity**

For this study, assessment of treatment emergent DLT will occur after a patient receives PVSRIFO and until 21 days ( $\pm$  3 days) after the first dose of pembrolizumab.

Peritumoral and CE occur frequently in rGBM and may be secondary to the disease process itself, surgical procedures, necrosis from previous radiation, or inflammation due to immune infiltration of the brain or destruction of tumor cells, which may manifest as neurologic dysfunction. Given that transient PTE has been observed following PVSRIFO use, the primary focus for DLT will be neurologic events meeting the criteria for a DLT defined as follows:

1.  $\geq$  Grade 3 neurologic events related to PTE or CE within the first 3 weeks of the first pembrolizumab administration that:
  - a. Do not resolve to  $\leq$  Grade 1 with the management practices outlined herein ( $\leq$  4mg/dexamethasone or 7.5 mg/kg bevacizumab) within 3 weeks of initiating such treatments,

and/or

- b. Require surgical debulking of the PVSRIFO infused tumor within 3 weeks of the first pembrolizumab administration

**To assess for any other potential DLT, CTCAE v5.0 will be utilized, and the following will also be considered DLT if treatment related:**

1. Any of the following SAEs:
  - a. Treatment-related death
  - b. Treatment-related life-threatening event
  - c. A medically significant condition (defined as an event that compromises patient safety or may require medical or surgical intervention to prevent one of the outcomes above).
  - d. Requires inpatient hospitalization or prolongation of existing hospitalization
  - e. Results in persistent or significant incapacity or substantial disruption to conduct normal life functions
2. Any Grade 4 non-hematologic toxicity
3. Any Grade 3 non-laboratory-based toxicity that is not reversible to its pre-PVSRIPO treatment baseline within 2 weeks of onset with the following exceptions:
  - a. Grade 3 fatigue lasting  $\leq$  3 days or Grade 3 fatigue in a participant with Grade 1 fatigue at baseline
  - b. Grade 3 diarrhea, nausea, or vomiting without use of anti-emetics or anti-diarrheals per standard of care
  - c. Grade 3 adrenal insufficiency due to suboptimal steroid replacement therapy
  - d. Grade 3 rash without use of corticosteroids or anti-inflammatory agents per standard of care

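### The SAP's DLT definition claims to follow the protocol but narrows attribution to lerapolturev, drops the overall time window for all but one item, and mis-references the SAE list

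*SAP*

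**What the plan says.** **Protocol.** The synopsis gives the purpose: "The study will begin with a safety lead-in for evaluation of dose-limiting toxicity (DLT) of the combination prior to full open enrollment". Section 7.4 sets the period: "assessment of treatment emergent DLT will occur after a patient receives" PVSRIPO (lerapolturev in the SAP), ending 21 days (± 3) after the first pembrolizumab dose. It then gives two lists. The first holds neurologic events, which must be related to peritumoral or cerebral edema. The second covers everything else, under the condition that "the following will also be considered DLT if treatment related"; its item 1 is the list of serious events. Section 7.1 adds that "Attribution of AEs/SAEs will be determined for each study intervention or concomitant medication/intervention", and names PVSRIPO and pembrolizumab among them. Section 2.1.2 places DLT assessment within the primary safety endpoint, for patients given PVSRIPO and at least one pembrolizumab dose.

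**SAP.** Section 3.2.6 merges the two lists under one sentence: "DLTs are defined per protocol as any of the following events related to lerapoltrev". Item 1 covers "neurologic events related to PTE or CE within the first 3 weeks of the first pembrolizumab administration that" fail to resolve or need debulking. No other item carries an assessment period. Item 5 admits laboratory "values only if meets one of the serious criteria outlined in 1 above or" if they persist or cause liver injury. Table 14.3.1.8 reports DLTs on the Safety Set, which SAP 4.2 defines by catheter placement.

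**Precedence.** Protocol Section 8 says the SAP governs where the two differ. SAP Section 6, which lists changes to the planned analyses, does not mention the DLT definition.

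**The concern.** A reader of the final report will take the DLT table as the protocol's DLT count for the combination, because the SAP says the definition is the protocol's. Followed as written, it is a different count. An event attributed to pembrolizumab alone loses its DLT status, although pembrolizumab is half of the regimen being assessed. An event attributed to lerapolturev long after the assessment period can gain DLT status. The two errors push in opposite directions, so the reader cannot tell whether the tabulated number is too high or too low. Because the SAP governs, the protocol text does not correct it.

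**Working it through.** The plan states no figure on this point, so there is none to reproduce. The check compares the texts, with day arithmetic for scale.

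| Element | Protocol 7.4 | SAP 3.2.6 |
|---|---|---|
| Attribution, neurologic item | Related to edema | Related to edema and to lerapolturev |
| Attribution, other items | Treatment related | Related to lerapolturev (2a and 2b still say treatment-related) |
| Window, neurologic item | 3 weeks from first pembrolizumab | Same |
| Window, all other items | To 21 ± 3 days after first pembrolizumab | None stated |
| Item 1 cited for seriousness | SAE list | Neurologic item (SAE list is now item 2) |
| Febrile neutropenia | Once, with criteria | Twice: item 6 without criteria, then a second entry numbered 5 with them |

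**Attribution.** Protocol 7.4 does not name the agent after treatment related. The stated purpose (the combination) and the agent-by-agent attribution in 7.1 support reading it as either study drug. A Grade 4 non-hematologic event on day 30, attributed to pembrolizumab alone, is then a DLT under the protocol and not under the SAP.

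The documents give neither a DLT rate nor the share *s* of DLTs attributed only to pembrolizumab. For scale, assume a true rate of 33% in 6 participants. The expected count under the SAP wording is 6 × 0.33 × (1 − *s*):
- *s* = 0: 1.98
- *s* = 0.10: 1.78
- *s* = 0.25: about 1.5
- *s* = 0.50: 0.99

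The proportion lost equals *s* whatever the rate.

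**Window.** Inputs are the first pembrolizumab dose on day 14 to 28 (Table 1, footnote 18), a DLT period of 21 ± 3 days after it, and a maximum follow-up of 730 days (Table 1), with infusion on day 0.
- Earliest close: 14 + 21 − 3 = day 32; 32/730 = 4.4%.
- Latest close: 28 + 21 + 3 = day 52; 52/730 = 7.1%.

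This uses the start in protocol 7.4 (PVSRIPO receipt). Protocol 3.1 and the synopsis start the period at the first pembrolizumab dose, which makes it 18 to 24 days long. The protocol contradicts itself on the start but not on the end. The SAP defines a treatment-emergent event as one on or after catheter placement, with no stated end beyond the study itself. Read literally, a lerapolturev-related hospitalisation at month 10 meets item 2d.

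**Cross-reference.** SAP item 1 contains no seriousness criteria, so the pointer in item 5 leads nowhere useful. The practical effect is small: a laboratory abnormality that met a seriousness criterion would normally be an SAE and qualify under item 2 directly.

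**Population.** The Safety Set can include people never infused and people infused but never given pembrolizumab. Protocol 3.2 keeps replaced participants out of the initial DLT assessment. Protocol 8.4.5 defines the primary safety analysis set as PVSRIPO plus at least one pembrolizumab dose.

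**The case against.** The strongest case for leaving the text alone has several parts.

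- *A window is present.* Item 1 has its 3 weeks, and footnote 3 of the SAP's schedule names the 21 ± 3 day DLT period. This stands against any claim that the SAP has no window at all. It does not rescue items 2 to 6, because the footnote concerns visit windows and is not linked to the definition or the table.
- *Combination DLTs are still counted.* Events judged related to lerapolturev, alone or jointly with pembrolizumab, remain in. A reader might infer that the table will not report the combination's DLTs; the documents support only that those attributed solely to pembrolizumab drop out.
- *Pembrolizumab toxicity is reported elsewhere.* SAP 5.8.1 summarises pembrolizumab-related events, serious events, and Grade 3 or higher and Grade 5 events. Table 14.3.1.10 covers immune-related events. So the event is not hidden; it loses its DLT label.
- *The lead-in decision is untouched.* One event is 1/3 = 33% or 1/6 = 17% of a lead-in cohort, so a reader might infer that a misclassified event could change the stopping decision. The documents do not support this. That decision is set in protocol 3.1 with DSMB review (9.3). The SAP describes a final analysis, its original version is dated 23 June 2022, and it already reports that full enrollment was not reached.
- *A denominator of about 30 cannot be assumed.* SAP Section 6 says the planned sample was not enrolled, and the Safety Set size is not given. Protocol 7.1.3 also ends event recording 30 days after a patient comes off study or leaves the per-protocol population, so 730 days is a ceiling and many participants will have less.
- *Limiting the table to the lead-in participants is a preference.* Protocol 8.4.5 plans DLT summaries without that limit. This stands.
- *Numbering and the duplicate item are editorial.* Largely true; a careful programmer would reach the intended reading.

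**Conclusion.** The concern holds as a reporting inconsistency. SAP 3.2.6 labels as the protocol's a DLT definition that differs from protocol 7.4 in attribution and in the time limit on items 2 to 6 and the thrombocytopenia exceptions. The change is undeclared, and the SAP takes precedence. Table 14.3.1.8 may omit DLTs attributed only to pembrolizumab. It may also include events after day 32 to 52, or in participants who never received the combination. The net direction is unknown, and the number of affected events cannot be derived from the documents; the expected counts above rest on assumed rates. The conclusion assumes that treatment related in protocol 7.4 means related to either study drug, and that the SAP is programmed as written. It should be corrected before the table is produced, but it does not call the lead-in decision into question.

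**What to change.** 1. In SAP 3.2.6, replace the lerapolturev-only condition with related to lerapolturev and/or pembrolizumab for the non-neurologic items, and return item 1 to the protocol's test of relation to edema.
2. Apply the protocol's assessment window to every item and to the thrombocytopenia exceptions. First reconcile its start, which differs between protocol 3.1 and the synopsis (first pembrolizumab dose) and protocol 7.4 (PVSRIPO receipt).
3. In item 5, change the reference from item 1 to item 2, and merge the two febrile neutropenia entries.
4. Tabulate DLTs in participants who received lerapolturev and at least one pembrolizumab dose, with the DLT-evaluable lead-in participants identified separately.
5. If any departure from protocol 7.4 is intended, list it with a reason in SAP Section 6 and remove the statement that the definition is the protocol's.

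The cost is a few lines of SAP text and one population flag. Agent-level attribution is already planned for collection under protocol 7.1, so no new data are needed.

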#### Concomitant Medications

Concomitant medications are those medications taken on or after catheter placement. This definition includes medications started prior to catheter placement but continuing concomitantly with lerapoltrev.

#### Prior Medications

Prior medications are defined as medications taken or therapies received by participants prior to catheter placement.

#### Immunotherapy Response Assessment in Neuro-Oncology (iRANO):

Note: While a modified version of iRANO is described in Section 8.4.6.1, Table 3 of the protocol, the definitions below, and used in the efficacy analyses, were based on iRANO without the modifications described in the protocol.

iRANO are guidelines that incorporate criteria previously defined by the RANO working committee to define CR, PR, SD, and progressive disease (PD) for participants with malignant glioma, low-grade glioma, and brain metastases. The key component of iRANO is specific additional guidance for the determination of PD among neuro-oncology participants undergoing immunotherapy. iRANO guidelines require confirmation of progression on follow-up imaging 3 months after initial radiographic progression if:

1. No new or significantly worsened neurologic deficits not due to co-morbid event or concurrent medication AND
2.  $\leq 6$  months from initiation of immunotherapy

If follow-up imaging confirms progression, the date of actual progression should be backdated to the date of initial radiographic progression. Appearance of new lesions solely does not define PD  $\leq 6$  months from initiation of immunotherapy. The lesions are added to the total lesion areas for follow-up assessments.

#### Complete Response (CR)

CR is defined as:

- Disappearance of all enhancing disease for  $\geq 4$  weeks AND
- No greater than physiologic steroids AND
- No new lesions AND
- Stable/improved T2/FLAIR AND
- Stable improved clinically

#### Partial Response (PR)

PR is defined by:

- $\geq 50\%$  decrease in the sum of biperpendicular diameters of enhancing disease for  $\geq 4$  weeks AND

- No new lesions AND
- Stable/improved T2/FLAIR AND
- Stable/improved steroids AND
- Stable/improved clinically

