#### 6.5.4.2 Bevacizumab

A clinically important feature of bevacizumab is the steroid-like improvement of the disrupted blood-brain barrier and reduction in PTE and mass effect when use in rGBM [26-28]. Given this and the success utilizing bevacizumab for the management of PTE or CE and related sequelae in prior studies with pembrolizumab [3] and PVSRIPO [5] and the combination in rGBM patients treated under compassionate use, eligible participants will be allowed to initiate bevacizumab treatment (7.5 mg/kg q 3 weeks) as early as 2 weeks after PVSRIPO infusion, at the time of the first planned pembrolizumab treatment. Bevacizumab use should be reevaluated as soon as

possible but at a minimum, after 3 consecutive doses (9 weeks) and be discontinued as soon as possible at the treating clinician's discretion.

Intermittent, short-term, lower dose bevacizumab use is not anticipated to have an appreciable impact on survival outcomes based on limited anti-tumor activity [26-28]. Given the impact of bevacizumab on enhancing lesions [29], all radiographic response will be confirmed  $\geq$  8 weeks after discontinuation of bevacizumab to account for the known radiographic pseudoresponse and T2/Fluid-Attenuated Inversion Recovery (FLAIR) will be monitored over time by independent radiographic reviewers blinded to patient outcome and bevacizumab use.

Branded Avastin® (bevacizumab) is preferred but if unavailable, MVASI™ (bevacizumab-awwb) is an acceptable alternative (check with Sponsor before utilizing any others). Bevacizumab will not be provided by the study.

**Risks Associated with Use:** There is a warning and precaution noted in the prescribing information of bevacizumab regarding risks of bleeding/wound healing complications within 28 days following major surgery. For this protocol, investigators will have the discretion to use low-dose bevacizumab at  $\geq$  2 weeks following the less invasive biopsy/intracranial infusion, if such use is judged by the investigator to be less than the potential risk of sequelae associated with PTE or CE after PVSRIPO treatment alone and/or followed by pembrolizumab. Bevacizumab is also associated with thromboembolic and other events; see the PI.

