## 3. GENERAL STATISTICAL CONSIDERATIONS

### 3.1. SAMPLE SIZE AND POWER

In an analysis of the ongoing Phase 1 study of lerapoltrev in rGBM, an ORR of 11% was demonstrated (7/61 participants achieved a complete response (CR) or partial response (PR); data on file, Istari). With 30 participants planned to be treated in this study, there is a greater than 75% power to demonstrate a 20% or greater improvement in ORR (ORR > 31%, two-sided  $P < 0.05$ ).

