### **5.3. CONCOMITANT MEDICATIONS**

All medication verbatim terms collected will be coded to Anatomical Therapeutic Classification (ATC) and preferred term (PT) using the World Health Organization (WHO) Data Dictionary (DD) Version Sep2020.

Concomitant medications, including bevacizumab and dexamethasone, will be summarized by presenting the number and percentage of participants by PT and ATC, using the safety set. Participants taking the same medication multiple times will only be counted once for that PT or ATC. Each summary will be ordered by descending order of incidence of ATC class and PT within each ATC class.

The number of participants who receive bevacizumab will be tabulated along with the number of doses administered, and dose levels received. Cumulative actual dose will be summarized. A participant's bevacizumab administration record will be included if it occurred after catheter placement and prior to the participant's Week 104, start date of subsequent anticancer therapy, or end of study/last contact date -- whichever occurs first. If a participant has bevacizumab listed as a post-study systemic monotherapy record, these data will be included in the analysis if the start and stop dates occur prior to any other type of subsequent anticancer therapy (eg, lomustine, pembrolizumab, irinotecan, nivolumab, carboplatin, etc.).

The number of participants who receive dexamethasone will be tabulated. The days on dexamethasone, cumulative actual dose, and average daily dose will also be summarized. Exposure will only be calculated from catheter placement to Week 104, start date of subsequent anticancer therapy, or until the participant's end of study/last contact date -- whichever occurs first.

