#### 5.7.1.1. Statement of Estimand

The **population for the trial** is defined through appropriate inclusion/exclusion criteria (IC/EC) to reflect the targeted participant population for approval. The analysis population is based on the efficacy analysis set.

The **treatment** of interest is lerapoltrev + pembrolizumab.

The **variable** of interest for ORR is the binary response value for a participant. For DOR, the variables of interest are the time from first response to confirmed progression/death/censoring.

The ability to evaluate treatment effect using the variables may be impacted by **intercurrent events** (ICEs). Death and use of additional cancer treatments may all impact the interpretation of treatment effect. For ORR, a composite strategy will be used to address intercurrent events (ICEs)

of potential death and start of additional cancer treatments, meaning occurrence of any of these events prior to a participant achieving CR or PR will mean the participant is considered a non-responder. DOR will use a composite strategy as well, treating death as an event that ends response, and the start of additional cancer treatments medications will be censored under the strategy.

The **population level summary measures** are the ORR, and the Kaplan Meier (KM) estimated median DOR, and associated CI for treatment.

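### The SAP's primary CR and PR definitions omit the protocol's 8-week off-bevacizumab confirmation, so pseudoresponses to the edema treatment can count toward ORR

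*SAP*

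**What the plan says.** **Protocol.** Section 6.5.4 makes low-dose bevacizumab the preferred edema treatment from 2 weeks after infusion. Section 6.5.4.2 requires all radiographic responses to be confirmed at least "8 weeks after discontinuation of bevacizumab to account for the known radiographic pseudoresponse". Table 3 item 4 applies the same condition to CR, PR and SD.

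The protocol is inconsistent about which criteria are primary. The synopsis objectives and Table 2 put the primary radiographic endpoints under iRANO and place Table 3, with the 8-week rule, in an exploratory row. Sections 2.1.1 and 8.4.6.1 instead base confirmed CR and PR on Table 3, and sections 2.3 and 8.4.6.1 call iRANO exploratory.

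**SAP.** Section 3.2.6 states that "the definitions below, and used in the efficacy analyses, were based on iRANO without the modifications described in the protocol". PR is a 50% or greater "decrease in the sum of biperpendicular diameters of enhancing disease for" at least 4 weeks, with no new lesions and stable or improved T2/FLAIR, steroids and clinical status. CR is built the same way. Neither mentions bevacizumab, and ORR is the proportion with CR or PR on these definitions.

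On intercurrent events, section 5.7.1.1 says: "Death and use of additional cancer treatments may all impact the interpretation of treatment effect". Either event before a response makes the participant a non-responder. Section 5.3 handles bevacizumab as a concomitant medication. Section 6 cancels the Table 3 analysis (item 3h, where it is called exploratory) and reports that central imaging review was not completed (item 2).

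**The concern.** The protocol gives its reason for the rule: bevacizumab changes enhancement, so a lesion can look smaller without an anti-tumor response. It also makes exposure likely. Bevacizumab is preferred over dexamethasone, and its use need only be re-evaluated after 3 consecutive doses (9 weeks). One ordinary course can therefore outlast the SAP's 4-week persistence window.

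The remaining SAP conditions do not clearly close the gap. The protocol credits bevacizumab with a steroid-like reduction of edema and mass effect, which may itself help a participant meet the T2/FLAIR, steroid and clinical conditions. The planned monitoring of T2/FLAIR by reviewers blinded to bevacizumab use is not available either.

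At stake is attribution. A response in the primary ORR could reflect the edema drug rather than lerapolturev plus pembrolizumab, and the tabulated ORR would not show which.

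**Working it through.** **1. Side by side.**

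| | Protocol 6.5.4.2 and Table 3 | SAP 3.2.6 |
|---|---|---|
| Persistence | at least 4 weeks | at least 4 weeks |
| Bevacizumab | confirmed at least 8 weeks after stopping | no condition |
| New lesions (CR/PR) | no condition | none allowed |
| T2/FLAIR (CR/PR) | no condition | stable or improved |
| Steroids, clinical status | conditions apply | conditions apply |

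Removing the second row alone can only add responders. Adding the third and fourth rows can only remove them.

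**2. The plan's own figure.** SAP 3.1 says: "With 30 participants planned to be treated in this study, there is a greater than 75% power". The target is an ORR of 31%, tested at a two-sided 5% level. The reference is 7/61 = 11.5%. With X binomial (n = 30) and an exact upper tail of at most 0.025:

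- P(X ≥ 7 | 7/61) = 0.0495, too large.
- P(X ≥ 8 | 7/61) = 0.0172, so the cut-off is 8/30.
- Power = P(X ≥ 8 | 0.31) = 0.757, which agrees with the stated figure.

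The Clopper-Pearson lower limit is 9.9% at 7/30 and 12.3% at 8/30. So 8 is also the smallest count whose exact 95% interval excludes 11.5%.

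**3. Effect of miscounting k participants.** Assume k true non-responders are counted as responders and the other 30 − k respond with probability 7/61. Then

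P(count ≥ 8) = P(Bin(30 − k, 7/61) ≥ 8 − k), and expected ORR = [k + (30 − k) × 7/61] / 30.

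| k | Expected ORR | P(at least 8/30) |
|---|---|---|
| 0 | 11.5% | 1.7% |
| 1 | 14.4% | 4.2% |
| 2 | 17.4% | 9.4% |
| 3 | 20.3% | 19.2% |
| 4 | 23.3% | 34.9% |

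**4. The same in terms of rates, all assumed.** Let u be the share given bevacizumab and s the share of treated non-responders who meet the SAP definition through pseudoresponse. Observed ORR = 7/61 + (54/61) × u × s.

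- u = 20%, s = 10%: 0.11475 + 0.88525 × 0.02 = 13.2%; chance of at least 8/30 is 3.7%.
- u = 40%, s = 25%: 0.11475 + 0.88525 × 0.10 = 20.3%; chance 25.4%.
- u = 60%, s = 40%: 0.11475 + 0.88525 × 0.24 = 32.7%; chance 81.5%.

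The width of this range comes from the inputs. It is not an estimate for this trial.

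**The case against.** **The SAP follows one of the protocol's two stated criteria, and the SAP governs.** Both parts are true. A reader might infer that the SAP overrode a settled primary criterion; the synopsis and Table 2 do not support that. But section 6.5.4.2 applies the rule to all radiographic responses, and it can be added to iRANO without adopting the rest of Table 3. Precedence settles which text applies, not whether the resulting response is attributable to treatment.

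**The change is disclosed.** It is, in general terms, in 3.2.6 and Section 6 item 3h, so a charge of concealment would fail. Neither place mentions the bevacizumab rule.

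**Pseudoresponses may not count in practice.** This stands in part. The other conditions still apply. Protocol 5.7.2 also has investigators record response by Table 3, and the SAP does not say whether iRANO response is re-derived or taken from those records. The supportable wording is that pseudoresponses can count, not that they do.

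**Bevacizumab may be an intercurrent event.** The term additional cancer treatments is undefined, and protocol Section 1 lists bevacizumab as approved for this disease. A reader might take the SAP 5.3 sentence "If a participant has bevacizumab listed as a post-study systemic monotherapy record, these data will be included in the analysis" as settling that it is not one. That sentence only governs which doses are tabulated. The ambiguity matters both ways: if bevacizumab is included, starting it before a response makes the participant a non-responder; if it is excluded, responses on it can count. Neither is the protocol's rule.

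**ORR need not be inflated against 11.5%.** This stands. The SAP's no-new-lesion and T2/FLAIR conditions can remove Table 3 responders, and the documents do not say whether the 7/61 were confirmed off bevacizumab.

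**Conclusion.** The point holds in this form: the SAP's primary CR and PR lack the off-bevacizumab confirmation that protocol 6.5.4.2 and Table 3 require, so a pseudoresponse to the preferred edema treatment can enter the primary ORR. The direction of this omission, taken alone, is certain: it can only raise ORR. The size is unknown, because the documents give no bevacizumab-use or pseudoresponse rate. The net shift against a Table 3 analysis is also unknown, so the documents do not show that the reported ORR will be too high overall.

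The illustration (1.7% rising to 4.2% with one miscounted participant and 9.4% with two) assumes 30 participants and a true ORR of 7/61. The 8/30 mark is derived here from the sample-size statement; the SAP's own analysis is descriptive, with exact intervals. SAP Section 6 says the full sample was not enrolled. Each miscounted response would therefore weigh more than 1/30 (3.3 percentage points) if the efficacy set is below 30, and the tabulated chances would not apply exactly. The stated power does not depend on this point.

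**What to change.** 1. **SAP 3.2.6, CR and PR.** Reconcile with protocol 6.5.4.2 by adding: a response first seen on bevacizumab, or within 8 weeks after its last dose, must be confirmed on MRI at least 8 weeks after the last dose; once confirmed, it is dated to its first observation.
2. **SAP 5.7.1.1.** State whether bevacizumab given for edema is an intercurrent event and how it is handled for ORR and DOR.
3. **Reporting.** Give ORR and DOR with and without responses first seen on, or within 8 weeks of, bevacizumab. Show responses with no qualifying off-bevacizumab scan as a separate category. Calling all of them non-responses could bias ORR downward.
4. **SAP Section 6.** State how the protocol's conflict over the primary criteria was resolved, and name the bevacizumab rule explicitly.

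The cost is SAP text and programming. Bevacizumab administration is already tabulated (Table 14.1.4.2) and lesion response is listed (16.2.6.2). The ORR may come out lower, and some responses may be unconfirmable because MRI is scheduled only every 9 to 12 weeks after Week 11. Sample size and treatment rules do not change.
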